## 7.5 Conducting the research

The sponsor or designated person will carry out the quality assurance and control activities of this research.. The monitor is responsible for supervising that data collection is done correctly, checking that the data collected in the CRD matches the source data and that the protocol is followed appropriately.

The sponsor will arrange for audits to be carried out as part of the implementation of quality assurance to ensure that the research is being carried out in accordance with this clinical research plan, standard operating procedures, good clinical practice (GCP) and all relevant regulatory requirements. The audits will be independent and will be carried out apart from the usual monitoring and quality control activities.

## 7.6 Monitoring plan

The study will be monitored to ensure that it is conducted and documented in accordance with the good clinical practice (GCP) protocol, and all applicable regulatory requirements.

Monitoring of the clinical study will be done through the following steps:

1. Verification of patient selection: The doctors at each center will be responsible for verifying that patients meet the inclusion and exclusion criteria of the clinical study. As patient randomization is done automatically through the platform, the risk of errors being made is very low.
2. Clinical research evaluation: The company monitor will review clinical research records for each site to ensure that it is conducted in accordance with the PIC, written procedures, and applicable regulatory requirements.
3. Data Quality Assessment: The company monitor will review patient records weekly to ensure that clinical and follow-up data are being collected and recorded correctly. In addition, the quality of the data provided by medical professionals will also be reviewed.
4. Notification of findings: Healthcare facilities will notify the company of any findings that may have implications for patient safety or data integrity.
5. Documentation and archiving: The sponsor and the health centers will maintain a complete record of all monitoring activities and will ensure that all records and documents related to the clinical study are properly archived.

## 8 Design and statistical analysis

### 8.1 Methodology and analysis

Specific subgroup analyzes will be performed based on the different baseline data and risk factors available for the project. We will also test interactions between each pair of subgroups and the main effect of treatment.

Independent t tests or Mann-Whitney U tests will be used to compare the questionnaire scores based on the distribution of the data, whether normally distributed or not, respectively.

The incidence of secondary endpoint events in the two study groups will be described using Kaplan-Meier survival curves, which will be compared using the log-rank test. The hazard ratio will also be obtained using Cox proportional hazards regression models comparing the TM and UC groups. The time of each event will be calculated from the day of registration. We will compare the number of readmissions and days of hospitalization between the two groups using the Wilcoxon rank sum test.

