#### 7.1.3 Variables

##### **Endpoint principal**

- Composite of quality of life, self-care and adherence to treatment by the patient (Change in the scale value of each questionnaire at 3 months)

The variables are quantified using validated scales. These measures are:

- Patient-Reported Self-Care Behavior Scale Measures (EHFScB Scale)
- Quality of life assessed through the "Minnesota Questionnaire for People with Heart Failure (MLHF questionnaire)"
- Patient adherence to treatment and medication intake (SMAQ Simplified Medication Adherence Questionnaire)

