##### **Secondary endpoints**

- Quality of life evaluated through the "Minnesota Questionnaire for People with Heart Failure" (Change in the value of the questionnaire scale at 3 months)
- Patient-Reported Self-Care Behavior Scale Measures (EHFScB Scale) (Change in Questionnaire Scale Value at 3 Months)
- Patient adherence to treatment and medication intake (SMAQ Simplified Medication Adherence Questionnaire) (Change in the value of the questionnaire scale at 3 months)
- Death from cardiovascular (CV) causes (Total number of patients who died in 3 months)

- Mortality from any cause (Total number of patients who died in 3 months)
- Acute HF decompensation (first and recurrent) during the follow-up period (Number of total decompensations in 3 months).

An acute decompensation of HF is defined as a new episode of symptoms and signs that requires intravenous decongestive treatment or increased oral diuretics either on an outpatient basis (e.g., day or home hospitalization for HF) or at home, emergency department or requiring an unplanned hospital admission.

- Hospital readmission due to HF decompensation (Total number of hospitalizations in 3 months)
- Hospital readmission for CV causes (Total number of hospitalizations in 3 months)
- Visits to the emergency room due to HF decompensation (Total number of visits to the emergency room in 3 months)
- Visits to the emergency room for CV causes (Total number of visits to the emergency room in 3 months)
- Medical care costs (Sum of costs for medication consumption, hospitalization, emergency care and medical transportation in 3 months)

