#### 7.1.4 Sample calculation

The sample calculation has been made based on the fact that a change of 5 points on the scale of the Minnesota Questionnaire for People with Heart Failure (MLHF questionnaire) between the control group and the experimental group (telemonitored) is clinically significant. (Rector, n.d.). Assuming an alpha risk = 0.05 and a beta error of 20%, we need to recruit a total of 253 participants divided into a control group and an experimental group.

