#### 7.2.1 Inclusion criteria

- Patients with heart failure (HF) with NYHA functional class  $\geq$  II (according to 2021 EU guidelines).
- Patients over 18 years of age.

- Patients who have suffered acute HF decompensation (first and recurrent) in the 30 days prior to enrollment in the study.

*\*An acute decompensation of HF is defined as a new episode of symptoms and signs that requires intravenous decongestive treatment or increased oral diuretics either on an outpatient basis (e.g., day or home hospitalization for HF) or at home, emergency department or requiring an unplanned hospital admission.*

- NT-pro BNP  $\geq 300$  pg/ml at study inclusion for patients without ongoing atrial fibrillation/flutter. If ongoing atrial fibrillation/flutter, NT-pro BNP should be  $\geq 600$  pg/mL
- Patients must have had an echocardiogram during their HF hospitalization or in the previous 12 months.
- Before starting any procedure, the hospital will ensure that the patient obtains an informed consent document.
- All patients will be eligible regardless of LVEF level: HFrEF, HFmrEF and HFpEF.
- Patients with minimal skills in handling mobile applications.

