### 7.3.1 Estimated recruitment time

Patients will be included in the study, based on the aforementioned eligibility criteria, for 3 months and will be monitored for 3 months. Each hospital will decide when to include their patients based on their particular clinical practice (either in the discharge planning process or during the first follow-up visit, i.e., approximately 1 week after discharge or after decompensation).

Medical professionals from each hospital will be in charge of recruiting participants. Patients will be recruited for 3 months.

Participants will be randomized in a 1:1 ratio to the control group (UC arm) or the intervention group (TM arm) at the recruitment stage. Randomization will be carried out at each center using the HumanITcare platform, which will indicate the arm to which each patient belongs. Stratification is performed with covariate adaptive randomization methods.

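### MLHF and EHFScB are compared without adjusting for baseline or the randomisation covariates, so the same patients could give a more precise answer, always in points

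*Combined protocol and SAP*

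**What the plan says.** Section 8.1 (Methodology and analysis) gives one rule for the questionnaires: "Independent t tests or Mann-Whitney U tests will be used to compare the questionnaire scores based on the distribution of the data", the choice turning on "whether normally distributed or not, respectively". No covariate is named. The only regressions in that section are Cox models for events; subgroup interaction tests are mentioned without a model for the main comparison.

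Section 7.1.3 defines the outcomes as changes. The composite primary is a "Change in the scale value of each questionnaire at 3 months". MLHF and EHFScB are also separate secondary endpoints; the MLHF entry reads "Change in the value of the questionnaire scale at 3 months". Section 7.1.4 sizes the trial on "a change of 5 points on the scale of the Minnesota Questionnaire for People with Heart Failure".

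Table 1 in section 9.1 has both scales recorded in both arms, at inclusion and at 3 months. Section 7.3.1 says of allocation: "Stratification is performed with covariate adaptive randomization methods". It does not list the covariates.

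**The concern.** Three features of the plan leave precision unused or the estimate unsettled.

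- **Baseline is not a covariate.** Section 7.1.3 speaks of change, section 8.1 only of scores, so either a change-score or a final-score t test could be run. In large samples ANCOVA is no less precise than either. A change score subtracts baseline with a fixed coefficient of 1; ANCOVA estimates the coefficient. Nothing here supports a value of 1. Eligibility requires "Patients who have suffered acute HF decompensation (first and recurrent) in the 30 days prior to enrollment in the study", and hospitals enrol at different moments, "either in the discharge planning process or during the first follow-up visit". Equal spread at baseline and Day 90 therefore cannot be taken for granted.
- **The balancing covariates are left out.** If they predict the analysed score, forced balance makes the two-sample test conservative: its standard error counts variation that the allocation has removed.
- **A lesser point.** If the Mann-Whitney branch is taken, the test does not estimate the 5-point mean difference used for sizing. A t test does, so this applies to that branch only.

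At stake is a missed or less precisely estimated effect on these two scales, one of which carries the sample size. The definition of the composite primary is a separate matter.

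**Working it through.** **Inputs from the documents.** Difference 5 points, alpha 0.05, beta 20%, total 253 (section 7.1.4); 1:1 allocation (7.1.1), so 126.5 per arm. Not given: SD, sidedness, dropout, the correlation r between baseline and Day 90, the ratio k = Day 90 SD / baseline SD, the balancing covariates, the number of centres. These are assumed below.

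**The plan's own figure.** 253 cannot be rebuilt without an SD. Solving backwards (two-sided, two-sample t power, 126.5 per arm, difference 5), 80% power needs an SD of 14.1 for the analysed variable, or 13.4 with 10% and 12.6 with 20% dropout. At 14.1 the 95% CI half-width is 3.50 points.

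**ANCOVA against a change-score t test with 80% power.** Variance ratio = k²(1 − r²) / (1 + k² − 2rk), which is (1 + r)/2 at k = 1. Example at k = 0.8, r = 0.5: 0.64 × 0.75 / (1 + 0.64 − 0.80) = 0.48/0.84 = 0.571. The reduction in interval width is 1 − √ratio.

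| k | r | variance ratio | ANCOVA power | interval narrower by |
|---|---|---|---|---|
| 1 | 0.5 / 0.7 / 0.8 | 0.750 / 0.850 / 0.900 | 90 / 86 / 84% | 13 / 8 / 5% |
| 0.8 | 0.5 / 0.7 / 0.8 | 0.571 / 0.628 / 0.640 | 96 / 94 / 94% | 24 / 21 / 20% |
| 1.25 | 0.5 / 0.7 / 0.8 | 0.893 / 0.981 / 1.000 | 84 / 81 / 80% | 5 / 1 / 0% |

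At k = 1 the half-width falls from 3.50 to 3.03, 3.23 and 3.32 points. There is no gain at k = 1.25, r = 0.8, because the regression slope rk is then exactly 1.

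**ANCOVA against a final-score t test with 80% power.** Variance ratio = 1 − r² = 0.75, 0.51, 0.36 at any k. Power is 90, 97.5 and 99.7%.

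**One fixed population.** Holding the SD of change at 14.1 implies a different population at each r (at k = 1, single-visit SDs of 14.1, 18.3 and 22.4). With both single-visit SDs held at an assumed 20, the SD is 20 for the final score, 20√(2(1 − r)) for change and 20√(1 − r²) for ANCOVA. Power, in that order:

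- r = 0.5: 51, 51 and 63%
- r = 0.7: 51, 72 and 79%
- r = 0.8: 51, 88 and 91%

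**Finite-sample check of the form proposed.** With 6,000 simulated trials per case, arms of 126 and 127, four uninformative covariates and HC3 robust standard errors, ANCOVA power at r = 0.5, 0.7, 0.8 was 0.889, 0.846, 0.824 (k = 1), 0.957, 0.938, 0.934 (k = 0.8) and 0.829, 0.788, 0.781 (k = 1.25). The change-score test had 0.795 to 0.800. Under the null (k = 1, r = 0.7, 10,000 trials) the size was 0.047 for change score, 0.047 for ANCOVA and 0.043 for ANCOVA with HC3.

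**Balancing covariates.** If they explain a share R² of the variance of the analysed score and balance is perfect, the unadjusted size is 2(1 − Φ(1.96/√(1 − R²))). For R² = 5, 10, 20% this is 4.4, 3.9, 2.8%. These are limits on the conservatism, and 20% is high for a change score. In a separate simulation (4,000 trials, 252 patients, a balanced six-level covariate explaining 10%, r = 0.5), size was 4.1% for the final-score t test, 4.7% for the change-score t test and 5.0% for ANCOVA; power was 80, 79 and 91%. The baseline and covariate gains overlap and must not be added.

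**Cost of useless terms.** With p uninformative terms, width grows by √((n − 3)/(n − p − 3)) times the ratio of t quantiles. For p = 5, 10, 20, 30 this is 1.0, 2.1, 4.3, 6.7% at n = 253, and 1.3, 2.6, 5.5, 8.6% after 20% dropout.

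**The case against.** The strongest reply is that this is an optional efficiency gain resting on assumed values. Since section 7.1.3 defines each outcome as change, the scores in 8.1 most naturally mean change scores, which already use baseline. The final-score figures should then be set aside. What remains at equal SDs is a 5 to 13% narrower interval, and almost nothing at k = 1.25 with r of 0.7 or more. In the recommended form, with robust standard errors and extra covariates, there can be a small loss (0.788 and 0.781 against about 0.80). Many centre terms could cancel the gain: with 30 useless terms at k = 1 and r = 0.8, 0.949 × 1.067 = 1.01, slightly wider than now. Covariates acting alike at both visits largely cancel in a change score, and the simulated 4.7% is within Monte Carlo error of 5%.

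Much of this stands. The change-score comparison is the one to rely on, the covariate-adaptive argument is weak for a change score, and the size of the gain cannot be read from the documents. It does not remove the point. No figure in the plan supports a slope of 1, the worst simulated loss is 1 to 2 percentage points against gains of up to about 16, and the change-score reading itself still has to be inferred.

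**Conclusion.** The point holds as a recommended improvement in precision, not as a fault in validity. Against a change-score t test with 80% power, adjustment would bring power to 84 to 90% at equal SDs, 94 to 96% if the Day 90 SD is 0.8 times baseline, and 80 to 84% if it is 1.25 times baseline, for correlations of 0.5 to 0.8. Robust standard errors and uninformative covariates take 1 to 2 percentage points off some of these, enough to turn the least favourable cases into a slight loss. The figures assume two-sided testing, no dropout and an SD solved backwards from 253; confidence in the size of the gain is therefore moderate. Its direction is firm unless the regression slope on baseline is close to 1 or many uninformative terms are added.

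**What to change.** In section 8.1, pre-specify for MLHF and EHFScB a linear model of the Day 90 score on arm, baseline score and the covariates used in the adaptive randomisation, with centre only if it is one of them. Report the adjusted mean difference in points with its 95% CI and a robust standard error. Drop the choice of test by observed distribution and keep Mann-Whitney as a sensitivity analysis. Name the randomisation covariates in section 7.3.1. This should be settled before outcome data are seen by arm.

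The cost is one paragraph, one list and slightly more analysis work; neither scale needs new data. The statistical cost is degrees of freedom. It is small with few terms, but the number of centres should be checked before centre is entered as many separate levels.

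The change does not define the composite primary. It also does not extend to SMAQ as the plan stands: the Day 0 and Day 90 lists for the TM arm in section 7.4 omit that questionnaire, while the same arm's questionnaire schedule and Table 1 include it. Those entries must be reconciled before a baseline-adjusted SMAQ analysis can be written.

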### Clinical data evaluation

Heart failure (HF) is a prevalent and fatal clinical syndrome that affects the quality of life of millions of people worldwide. Between 17% and 45% of patients with HF die within the first year and the rest die within 5 years (Tripoliti et al., 2017). Furthermore, these patients have a high risk of rehospitalization, their associated healthcare costs are enormous, and the longer the life expectancy, the higher the prevalence of the disease. (McDonagh et al., 2021). Symptoms of IC commonly include shortness of

breath, excessive tiredness, and swelling of the legs that may worsen with decompensation. (Schiff et al., 2003), so traveling to medical centers represents a disadvantage for these people. Remote monitoring technologies provide a feasible solution that allows for earlier identification of decompensation and better adherence to lifestyle changes and medication (Brahmbhatt & Cowie, 2019). Although telemonitoring using smartphones shows potential to reduce both the frequency and duration of hospitalizations for HF (Koulaouzidis et al., 2016) cannot be associated with reduced mortality from any cause (Koehler et al., 2011). Therefore, there is a need to search for more effective and precise methodologies. In recent years, the use of portable devices (wearables) that allow daily monitoring of the patient's physiological data combined with Artificial Intelligence (AI) has shown enormous potential to predict diseases related to the cardiovascular system, their adverse events and the patient's health status (Lee et al., 2022), including patients with HF (Guidi et al., 2015).

HumanITcare is a platform that allows this remote monitoring through the integration of different medical devices and self-reported data. The platform allows you to customize a monitoring plan so that healthcare professionals can adapt this tool to the needs of a specific patient group or at the individual patient level.

The HumanITcare platform has been used in different therapeutic areas to improve personalized patient monitoring. Some of the areas in which an improvement in patient monitoring and health status has been demonstrated would be cardiology (IC - (Sanchez et al., 2020); cardiac rehabilitation - (Calvo-López et al., 2023), palliative care (Castillo Padrós et al., 2022), respiratory diseases, or oncology, among others.

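### Section 8.1 uses Kaplan-Meier to describe the incidence of first readmissions, emergency visits, decompensations and CV death; with death as a competing event this slightly overstates incidence

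*Combined protocol and SAP*

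**What the plan says.** Section 8.1 gives one time-to-event approach for all the clinical events: "The incidence of secondary endpoint events in the two study groups will be described using Kaplan-Meier survival curves". The curves are compared by a log-rank test, and "The hazard ratio will also be obtained using Cox proportional hazards regression models comparing the TM and UC groups". On timing, the section says only that "The time of each event will be calculated from the day of registration". It states no censoring rule. Numbers of readmissions and days in hospital are compared separately by a rank sum test.

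Section 7.1.3 lists the events. Several exclude death by definition, for example "Hospital readmission due to HF decompensation (Total number of hospitalizations in 3 months", "Hospital readmission for CV causes (Total number of hospitalizations in 3 months" and "Visits to the emergency room due to HF decompensation (Total number of visits to the emergency room in 3 months"; CV emergency visits and acute decompensation do so too. One fatal endpoint is cause-specific: "Death from cardiovascular (CV) causes (Total number of patients who died in 3 months". All-cause mortality is listed separately.

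Death otherwise appears as a withdrawal criterion (7.2.3) and as a recorded clinical event (7.4 and Table 1). No section mentions competing risks, cumulative incidence functions, or a composite of these events with death.

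The only mortality figure is in section 4, under clinical data evaluation: "Between 17% and 45% of patients with HF die within the first year".

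**The concern.** A patient who has died cannot be readmitted. If that patient is censored at death, Kaplan-Meier treats them as still able to have the event and as represented by those who remain at risk. One minus the curve then estimates how often the event would occur if nobody died first. That is not the share of randomised patients who have the event, which is what a reader takes incidence to mean. With complete follow-up, the Aalen-Johansen estimate equals patients with the event divided by patients randomised. Kaplan-Meier exceeds it as soon as anyone who is still event-free dies before others have the event.

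Deaths are to be expected. Patients enter within 30 days of a decompensation (7.2.1), and the 3-month window was chosen because relapse and harm are more likely then (7.1.2). The synopsis names a lower incidence of the main critical heart failure events as something the study will measure, and section 16.2 sends the results into the clinical evaluation. The incidence figures should therefore mean what they appear to mean.

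**Working it through.** **The plan's own figures.** The documents give no event rate for these endpoints, so there is no stated incidence to reproduce. The one design figure, 253 participants, comes from a 5-point difference on the Minnesota questionnaire. No standard deviation is given; two-sided and without dropout, 253 implies 5 / [(1.960 + 0.842) × √(2/126.5)] ≈ 14.2 points. Nothing below depends on it except the arm size of about 126.5.

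**Inputs**
- One-year mortality 17% to 45%: section 4.
- Follow-up 3 months: section 7.1.2.
- Constant hazards: assumption.
- Kaplan-Meier 3-month event rate K of 20%, 30% or 40%: assumption.
- Share of deaths that are non-CV, 10% to 40%: assumption.

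**Step 1: mortality at 3 months.** The cumulative death hazard is D = −ln(1 − annual mortality)/4.
- 17%: D = 0.0466, so 1 − 0.83^0.25 = 4.6% dead.
- 45%: D = 0.1495, so 1 − 0.55^0.25 = 13.9% dead.

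**Step 2: true cumulative incidence.** With E = −ln(1 − K), cumulative incidence = E/(E + D) × [1 − exp(−(E + D))].

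Example with K = 30% and 13.9% deaths: E = 0.3567 and D = 0.1495, so E/(E + D) = 0.705 and 1 − exp(−0.5062) = 0.397. The product is 0.280, and Kaplan-Meier overstates by 2.0 points.

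| Deaths at 3 months | K = 20% | K = 30% | K = 40% |
|---|---|---|---|
| 4.6% | 19.6% (over by 0.4) | 29.4% (0.6) | 39.2% (0.8) |
| 13.9% | 18.6% (1.4) | 28.0% (2.0) | 37.4% (2.6) |
| 20% (assumed, if early risk is higher) | 18.0% (2.0) | 27.1% (2.9) | 36.2% (3.8) |

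In relative terms the excess is about 2% in the first row and 7% in the second. A simulation of 400,000 patients at K = 30% and 13.9% deaths gave 30.0% by Kaplan-Meier and 28.0% observed.

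**Step 3: CV death.** With total mortality m and non-CV share s, cumulative incidence = (1 − s)m, and Kaplan-Meier gives 1 − (1 − m)^(1 − s). At m = 13.9% and s = 40% these are 8.34% and 8.59%, a gap of 0.25 points. At m = 4.6% and s = 10% the gap is 0.01 points.

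**Step 4: difference between arms.** Take the same event hazard in both arms (K = 30%), with 4.6% deaths in one and 13.9% in the other. Kaplan-Meier shows 30% in both. The true incidences are 29.4% and 28.0%, so the overstatement is 0.6 points in one arm and 2.0 in the other. With closer mortality (assumed 6% and 8%, K = 25%), the overstatements are 0.72 and 0.97 points and differ by only 0.24.

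**Step 5: sampling error for comparison.** √[p(1 − p)/126.5] is 3.6 points at 20%, 4.1 at 30% and 4.4 at 40%. For a difference between two arms at 25% it is √2 × 3.85 = 5.4 points.

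**The case against.** The strongest reply is that this is too small to matter. Every overstatement in the table is below the standard error for one arm, and much of it cancels between arms when mortality is similar. The curves are descriptive and the endpoints secondary. Section 7.1.3 defines the endpoints as totals over a fixed 3 months, which can be reported directly and do not pass through Kaplan-Meier. The mortality range is a background figure for heart failure in general. The exclusions and the need for mobile skills may put this trial below its upper end, although recent decompensation points the other way. Censoring at death is also not written down; it is the default when nothing else is said.

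Most of this stands, and it limits the size and reach of the point. It does not remove it. The plan still describes the Kaplan-Meier curves as incidence, and the direction of the error is known and avoidable.

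Four stronger readings go beyond the documents:
- **The treatment comparison is invalid.** It is not. Log-rank and Cox with censoring at death compare cause-specific hazards and remain valid for that purpose. They do not measure the effect on cumulative incidence.
- **The arm with more deaths always has the larger bias.** This holds only at similar event hazards. At K = 40% with 4.6% deaths the overstatement is 0.84 points; at K = 20% with an assumed 7% deaths it is 0.68.
- **Only deaths from other causes compete.** That is right for CV death alone. For readmissions, emergency visits and decompensation, any death competes, including one from heart failure.
- **Cumulative incidence curves would cover every event endpoint.** They describe first events, not the recurrent decompensations and total counts in 7.1.3.

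**Conclusion.** The point holds as a modest correction to how incidence is described. As section 8.1 is written, Kaplan-Meier overstates the 3-month incidence of first non-fatal events by about 0.4-2.6 points (2-7% relative), which is roughly 0.5 to 3.3 patients in an arm of 126.5. For CV death the overstatement is at most about 0.25 points, which is negligible. All-cause mortality is unaffected.

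These sizes rest on the plan's background mortality, a constant hazard, assumed event rates of 20-40% and an assumed non-CV share of 10-40%. If early mortality were 20%, the gap would be 2.0-3.8 points, still below the standard error for one arm. The direction needs none of these figures, only that some event-free patients die during follow-up and that no other rule for death is applied.

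A reader might infer that the trial's conclusion on clinical events is at risk. The documents do not support that: the hazard comparisons stand and no conclusion is shown to change.

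**What to change.** In section 8.1:
- State how death is handled for each event endpoint.
- For time-to-first-event displays of readmission, emergency visits and decompensation, replace Kaplan-Meier by Aalen-Johansen cumulative incidence curves with death from any cause as the competing event. Do the same for CV death, with non-CV death competing. Show the curve for the competing death alongside.
- Keep the log-rank test and Cox model for these endpoints, and label the results cause-specific hazard ratios.
- Keep Kaplan-Meier for all-cause mortality.
- Say that these curves concern first events. The recurrent and total counts in 7.1.3 are not covered by this change.

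The cost is a wording change and a little more analysis work in standard software. The extra information needed is the date and cause of death, which section 7.4 and Table 1 already collect in both arms. The sample size does not change. The stated incidences become slightly lower.
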